6.3.3.3 Reporting Adverse Events

All AEs reported or observed during the study will be recorded on the AE page of the eCRF. Information to be collected includes drug treatment, dose, event terminology, date of onset, CTCAE Version 4.0 assessment of severity and relationship to study drug, date of resolution of the event, seriousness, any required treatment or evaluations, and outcome. With the exception of disease progression, AEs resulting from concurrent illnesses, reactions to concurrent illnesses, and reactions to concurrent medications also must be reported. All AEs will be followed to adequate resolution. CTCAE Version 4.0 will be used to grade all AEs (Section 6.3.3.4).

Any AE that meets SAE criteria (Section 6.3.3.1) must be reported to the contract research organization (CRO) immediately (i.e., within 24 hours after the time site personnel first learn about the event). The following contact information is to be used for SAE reporting:

ADCT-402-102 Protocol Amendment 3

6.3.3.4 Assessment of Severity

Adverse events will be graded according to CTCAE Version 4.0. For events not included in the CTCAE criteria, the severity of the AE is graded on a scale of 1 to 5, as shown in Table 3.

Table 3. Definition of Severity Grades for Common Terminology Criteria for Adverse Events (CTCAE)

Grade	Definition
1	Mild; asymptomatic or mild symptoms; clinical or diagnostic observations only; intervention not indicated
2	Moderate; minimal, local or non-invasive intervention indicated; limiting age-appropriate instrumental ADL ^a
3	Severe or medically significant but not immediately life-threatening; hospitalization or prolongation of hospitalization indicated; disabling; limiting self-care ADL ^b
4	Life-threatening consequences; urgent intervention indicated
5	Death related to adverse event

a Instrumental activities of daily living (ADL) refer to preparing meals, shopping for groceries or clothes, using the telephone, managing money, etc.

Changes in the severity of an AE should be documented to allow an assessment of the duration of the event at each level of intensity to be performed. Adverse events characterized as intermittent do not require documentation of onset and duration of each episode.

6.3.3.5 Assessment of Causality

The Investigator's assessment of an AE's relationship to study drug is part of the documentation process, but it is not a factor in determining what is or is not reported in the eCRF. All AEs, regardless of assessment of causality, are reported in the eCRF.

All SAEs considered at least possibly related to the study drug will be considered unexpected; and therefore, reported as suspected unexpected serious adverse reactions (SUSARs).

6.3.3.6 Follow-Up of Patients Reporting Adverse Events

All AEs must be reported in detail on the appropriate page of the eCRF and followed to satisfactory resolution, until the Investigator deems the event to be chronic or not clinically significant, or until the patient is considered to be stable.

b Self-care ADL refer to bathing, dressing and undressing, feeding self, using the toilet, taking medications, and not bedridden.

ADCT-402-102 Protocol Amendment 3

6.3.4 Pregnancy

Any pregnancy that occurs during study participation must be reported using a clinical study Pregnancy Report Form. To ensure patient safety, each pregnancy must be reported as described for reported AEs in Section 6.3.3.3, upon learning of its occurrence. The pregnancy must be followed to determine outcome (including spontaneous miscarriage, elective termination, normal birth, or congenital abnormality) and status of mother and child, even if the patient was withdrawn from the study. The outcome of the pregnancy will be reported on the Pregnancy Outcome Form. Spontaneous miscarriages must be reported as an SAE.

Any SAE occurring in association with a pregnancy brought to the Investigator's attention after the patient has completed the study and considered by the Investigator as possibly related to the study treatment must be promptly reported (Section 6.3.3.3).

6.3.5 Clinical Laboratory Analyses

Samples will be collected at the time points specified in the Schedule of Events for the Q3W and QW dosing schedules (Table 5 and Table 7, respectively) Appendix 12.1.

Any clinically significant abnormal laboratory test results are to be recorded as AEs or SAEs, per CTCAE Version 4.0.

6.3.5.1 Hematology

The complete blood count (CBC) includes WBC with a 5-part differential, platelet count, hemoglobin, hematocrit, and ANC. Peripheral blasts will be included in the hematology analysis for Part 2 only. If the WBC value is <400 x 10⁶/L, a differential is not required. The coagulation panel must include partial thromboplastin time (PTT) and International Normalized Ratio (INR); prothrombin time (PT) expressed in seconds is optional. Patients taking coumarin-derivative anticoagulants should be monitored closely and their anticoagulant dose adjusted as needed.

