- 13. Hematology: CBC to include WBC with a 5-part differential, platelet count, hemoglobin, hematocrit, and ANC. Peripheral blasts will be included in the hematology analysis for Part 2 only. If WBC is < 400 x 106/L differential is not required.
- 14. Samples for hematology, coagulation panel, biochemistry, and urinalysis will be collected prior to dosing unless the last sample was collected: <24 hours before the start of ADCT-402 infusion on Day 1 of Cycle 1, or <72 hours before the start of ADCT-402 infusion on Day 1 of Cycle 2 and subsequent cycles.
- 15. Coagulation panel: PTT and INR; PT expressed in seconds is optional.
- 16. Biochemistry: Alanine aminotransferase, aspartate aminotransferase, gamma-glutamyl transferase, alkaline phosphatase, amylase, lipase, total bilirubin, sodium, potassium, calcium, magnesium, blood urea nitrogen or urea, carbon dioxide/bicarbonate, chloride, creatinine, creatine phosphokinase, total protein,

- albumin, glucose, triglycerides, total cholesterol, phosphorus, and lactate dehydrogenase. At Days 1, 8 and 15 of each cycle, biochemistry will include creatinine clearance (calculated using the Cockcroft and Gault formula [Cockcroft and Gault, 1976]).
- 17. Urinalysis to include: pH, specific gravity, protein, glucose, ketones, nitrites, occult blood and bilirubin. The urinalysis may be performed using a urine dipstick.
- 18. 12-lead ECG: On Days 1 and 2 of Cycles 1 and 2, a 12-lead ECG is to be performed before the start of the ADCT-402 infusion, within 30 minutes of the end of infusion, and 3 hours (± 30 minutes) and 24 (± 2.4) hours after the end of infusion.
- 19. 12-lead ECG: On Day 1 of Cycle 3 and subsequent cycles, a 12-lead ECG is to be performed before the start of ADCT-402 infusion.
- 20. Concomitant medications to include prescription or over-the-counter medication, herbal or naturopathic products within the 14 days prior to the Cycle 1, Day 1 visit, during the study, and 30 days following the patient's last dose of ADCT-402.
- 21. Premedication to be performed if a CTCAE Grade 2 or higher infusion-related hypersensitivity reaction is observed in 1 patient at any time during Part 1 of the study. All subsequent patients must receive prophylactic treatment on Days 1, 8 and 15 of each cycle thereafter to reduce the risk of hypersensitivity reaction (Section 5.2).

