## 4 Statistical methods

All analyses use SAS® version 9.4 or higher. Summary tables will be organized by each dose level; if some dose levels have only a few subjects, then dose levels can be combined into dose ranges. All available data will be used in the analyses, and important data will be included in data listings, sorted by dose level, subject, and by visit within subject. Missing data will not be imputed, except via censoring in survival analyses and as otherwise specified.

Unless otherwise noted, categorical data will be presented using counts and percentages, with the number of subjects in the analysis set by treatment group as the denominator for percentages. Percentages will be rounded to one decimal place, except 100% will be displayed without any decimal places, and percentages will not be displayed for zero counts. Continuous data, unless otherwise noted, will be summarized using the number of observations (n), mean, standard deviation (std), median, minimum, and maximum. Minima and maxima will be rounded to the precision of the original value, and means, medians, and confidence intervals (CIs) if presented will be rounded to 1 decimal place greater than the precision of the original value. The std will be rounded to 2 decimal places greater than the precision of the original value, up to a maximum of 3 decimal places.

No hypothesis testing will be performed in this study.

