### 4.8.3 Laboratory Data

Descriptive statistics (mean, standard deviation, median, and range) will be calculated for the raw data and for their changes from baseline at each scheduled assessment.

All results will be summarized using shift from baseline. Shifts for clinical laboratory results that can be graded according to CTCAE version 4.0 will be summarized by CTCAE grade.

Summaries by visit will include data from scheduled assessments, and all data will be reported according to the nominal visit date for which it was recorded. Unscheduled data will be included in “worst case post baseline” summaries, which will capture a worst case across all scheduled and unscheduled visits after the first dose of study treatment.

Laboratory data, including urinalysis, will be listed. Pregnancy test results will not be listed, but will be included in datasets.

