##### Handling of missing severity/grades of AEs

If the severity/grade is missing for one of the treatment emergent occurrences of an AE, the maximal severity of the remaining occurrences will be considered. If the severity is missing for all the occurrences a “missing” category will be added in summary table.

No other imputation of values for missing data will be performed.

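### ANC may be missing when WBC is below 0.4 x 10^9/L, and the SAP has no rule to count such samples as Grade 4 neutropenia in the laboratory tables

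*Protocol*

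**What the plan says.** **Protocol.** Section 6.3.5.1 defines the blood count: "The complete blood count (CBC) includes WBC with a 5-part differential, platelet count, hemoglobin, hematocrit, and ANC". It then adds a waiver: "If the WBC value is <400 x 10⁶/L, a differential is not required". Footnote 13 of Tables 5 and 7 repeats it for both dosing schedules. None of these places says whether ANC, which is listed as its own item, is still expected when the differential is omitted.

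**SAP.** Section 4 sets the general rule: "Missing data will not be imputed, except via censoring in survival analyses and as otherwise specified". Section 6.1.1 gives rules for a missing AE relationship and a missing AE grade, and closes with: "No other imputation of values for missing data will be performed". Section 4.8.2.1 adds a rule for incomplete AE onset dates. No section gives a rule for a missing laboratory value.

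Section 4.8.3 plans descriptive statistics by visit and shift tables: "Shifts for clinical laboratory results that can be graded according to CTCAE version 4.0 will be summarized by CTCAE grade". It also plans a worst-case summary, "which will capture a worst case across all scheduled and unscheduled visits after the first dose of study treatment".

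**The concern.** ANC is usually calculated from the differential (general laboratory practice; the documents do not say so). A site that omits the differential at a very low WBC may therefore report no ANC and still comply with the protocol. Such a value would be missing because the count is so low, not by chance. Its grade is also not in doubt, because the WBC on the same sample settles it.

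Under the SAP as written, such a sample contributes no ANC and no neutrophil grade. The shift and by-visit tables would omit samples that are certain to be Grade 4. Safety is a primary endpoint (Protocol 7.2.1), and after early termination the SAP only lists efficacy (section 4.9). The safety tables are therefore the main statistical output, and a one-directional gap in the post-baseline neutrophil tables is worth closing.

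**Working it through.** **The plan's own figure.** The only computed probability in the documents is in Protocol 7.3: a true AE rate of 15%, 10 patients, 80%. It reproduces as 1 − 0.85^10 = 0.803, the chance of at least one event (exactly one would be 10 × 0.15 × 0.85^9 = 0.347). It is not disputed. It concerns Part 2 cohorts, which SAP 3.3 says will not be analysed, and serves below only as a familiar scale.

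**Step 1: the threshold.** 400 x 10^6/L ÷ 10^9 = 0.4 x 10^9/L.

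**Step 2: the bound.** Neutrophils are part of the white count, so ANC ≤ WBC < 0.4 x 10^9/L. The CTCAE v4.0 Grade 4 limit is taken as 0.5 x 10^9/L (assumption; not printed in the documents). Every sample under the waiver is then Grade 4.

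**Step 3: by-visit tables.** Let G be the true Grade 4 share at a visit, w the share of patients with WBC below 0.4, and u the share of those without ANC. The documents give none of these. SAP section 4 by default takes percentages of the whole analysis set, so the reported share is G − w × u. The loss in percentage points is:

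| w | u = 0 | u = 0.5 | u = 1 |
|---|---|---|---|
| 10% | 0 | 5 | 10 |
| 25% | 0 | 12.5 | 25 |
| 50% | 0 | 25 | 50 |

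If only non-missing values form the denominator, the reported share is (G − wu)/(1 − wu). With G = 60%, w = 25% and u = 1, the default gives 35% and the non-missing denominator gives 0.35/0.75 = 46.7%. With u = 0.5 the two are 47.5% and 0.475/0.875 = 54.3%. Neither version can exceed G. Mean ANC rises whenever the recorded values average above the omitted ones. That is the expected case, since recorded values are not capped at 0.4.

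**Step 4: worst-case table.** A patient's Grade 4 disappears only if every one of that patient's Grade 4 samples lacks ANC. If each lacks it independently with probability q, the chance for a patient with k such samples is q^k:

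| q | k = 1 | k = 2 | k = 3 |
|---|---|---|---|
| 0.25 | 25% | 6.2% | 1.6% |
| 0.50 | 50% | 25% | 12.5% |
| 0.75 | 75% | 56% | 42% |

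Correlation within a patient moves the loss back towards q.

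**Step 5: patient-level rate.** If a share m of Grade 4 patients is lost in this way, a true rate P is reported as P × (1 − m). With P = 15%:

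| m | Reported rate | Chance of at least one in 10 |
|---|---|---|
| 0 | 15% | 80.3% |
| 0.10 | 13.5% | 76.5% |
| 0.25 | 11.3% | 69.7% |
| 0.50 | 7.5% | 54.1% |

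**Step 6: dose pattern.** Assume true rates of 30% (low dose) and 60% (high dose).

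- Equal m = 0.25 gives 22.5% and 45%.
- m = 0.10 and 0.40 gives 27% and 36%.
- m = 0 and 0.50 gives 30% and 30%.

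The order reverses only if m at the high dose exceeds 1 − 0.5 × (1 − m at the low dose), which is above 0.55 when the low-dose m is 0.10.

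**Step 7: baseline.** SAP 4.8 takes the latest recorded value up to the first dose as baseline. If the Day 1 ANC is missing under the waiver, an earlier and possibly higher value is used, and the later fall looks larger. The entry criteria set no lower limit for WBC or ANC, so this can occur. The understatement therefore applies to post-baseline summaries, not to every change from baseline.

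**The case against.** **ANC is a separate item.** The waiver names only the differential and makes it optional. A site or analyser may still report ANC, and then nothing is lost. This stands: the text supports ANC that may be missing, not ANC that is missing.

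**Other routes show the toxicity.** Protocol 6.3.5 says: "Any clinically significant abnormal laboratory test results are to be recorded as AEs or SAEs, per CTCAE Version 4.0". AEs are then tabulated by maximum CTCAE grade (SAP 4.8.2.1). The low WBC itself is recorded, summarised and listed. A reader might infer that Grade 4 neutropenia is under-reported across the trial. The documents do not support that; the gap is in the laboratory ANC tables. The AE route depends on the investigator's judgement of clinical significance, so it does not replace those tables.

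**The worst-case rule recovers patients.** One recorded Grade 4 ANC at any visit is enough. This stands for that table but does not restore the by-visit and shift tables.

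**DLTs.** A reader might infer that the hematologic DLT record is broken. It is not derived from these tables: the steering committee determines DLTs (Protocol 6.3.2), the definition also requires marrow findings (6.3.1), and the SAP only lists them (4.8.1). The same bound tells the investigator the neutropenia grade.

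**Consequence.** Only Part 1 is analysed, there is no hypothesis testing, and laboratory data are listed. This argues for a lower severity, not for leaving the gap.

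**Conclusion.** The concern holds in limited form. If a site uses the waiver and reports no ANC, the SAP's rules leave a sample of known grade out of the by-visit ANC summaries and the shift tables, and possibly leave the patient's Grade 4 out of the worst-case table. Post-baseline laboratory summaries would then understate neutropenia.

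The conclusion rests on the assumed Grade 4 limit of 0.5 x 10^9/L and on some waived samples lacking ANC. The size runs from nothing (every waived sample has an ANC) to the full share of patients with WBC below 0.4 at a visit (none has). The documents give neither share.

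Two stronger readings are tempting: that the loss is greatest at the most myelosuppressive doses, even reversing the dose order, and that the bias always favours the drug. A loss that rises with dose is plausible, but no document figure shows it, and reversal needs the strongly unequal losses of step 6. The baseline rule can work in the other direction. Severity: minor to moderate.

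**What to change.** 1. In SAP 4.8.3 and 6.1.1, add a rule: where ANC is missing and WBC on the same sample is below 0.4 x 10^9/L, count neutrophils as Grade 4 in the shift and worst-case tables. Apply the same rule at baseline. Describe it as a logical bound, so that it does not conflict with the ban on imputation.
2. In numeric summaries, show the value as '<0.4' and report medians.
3. Give the number of such records by dose level. This also shows whether the gap mattered.
4. State in the protocol or the laboratory instructions whether the waiver covers ANC.

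The cost is a few sentences in the SAP and one derivation. The downside is a few assigned grades, to be footnoted. If ANC was always reported, the rule never applies and the tables do not change.

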6.3.5.2 Biochemistry

Tests for clinical biochemistry include alanine aminotransferase, aspartate aminotransferase, gamma-glutamyl transferase, alkaline phosphatase, amylase, lipase, total bilirubin, sodium, potassium, calcium, magnesium, blood urea nitrogen or urea, carbon dioxide/bicarbonate, chloride, creatinine, creatine phosphokinase, total protein, albumin, glucose, triglycerides, total cholesterol, phosphorus, and lactate dehydrogenase. Biochemistry will also include creatinine clearance (Cockcroft and Gault, 1976).

6.3.5.3 Urinalysis

Urinalysis analytes will include pH, specific gravity, protein, glucose, ketones, bilirubin, nitrites and occult blood. The urinalysis may be performed using a urine dipstick.

ADCT-402-102 Protocol Amendment 3

6.3.5.4 Additional Renal Function Studies

Urine will be collected for central laboratory testing of biomarkers suggestive of potential renal injury (aquaporin-2, calbindin D28, and clusterin). Analysis of this additional urine sample will be performed at a central laboratory (instructions provided in the Laboratory Manual).

6.3.6 Electrocardiograms

A 12-lead ECG is to be performed at the time points identified in the Schedule of Events for the Q3W and QW dosing schedules (Table 5 and Table 7, respectively) in Appendix 12.1. Any abnormalities, including those that worsen from baseline, believed to be clinically significant in the medical and scientific judgment of the Investigator are to be recorded as AEs or SAEs.

Measurement of the QTc interval may be obtained according to the formula used by the institution, however, the Fridericia formula is preferred (Fridericia, 1920). The same formula used to confirm eligibility must be applied within a patient for the duration of the study.

6.3.7 Physical Examination

Physical examinations will include a complete review of body systems, including whole body skin assessment. Whole body skin assessment does not have to be performed by a dermatologist. However, any unexplained lesion is to be referred to a dermatologist for further evaluation and biopsy if clinically warranted. Any clinically significant abnormalities, including those that worsen from baseline, are to be recorded as AEs or SAEs.

6.3.8 Vital Sign Measurements

Vital signs measurements will include arterial blood pressure, heart rate, respiratory rate, and temperature. Any clinically significant abnormalities, including those that worsen from baseline, are to be recorded as AEs or SAEs.

6.3.9 Weight

If possible, patients are advised to monitor their weight daily starting Cycle 1 Day 1 and inform their investigator if their weight increase more than 1 kg (2.2 lbs) from Cycle 1 Day 1.

6.3.10 Eastern Cooperative Oncology Group Performance Status

The patient's performance status will be assessed according to the time points in the Schedule of Events for the Q3W and QW dosing schedules (Table 5 and Table 7, respectively) in Appendix 12.1 using ECOG performance status grades (Table 4; Oken, 1982).

ADCT-402-102 Protocol Amendment 3

Table 4. Definition of Eastern Cooperative Oncology Group (ECOG) Performance Status Grades

Grade	Definition
0	Fully active, able to carry on all predisease performance without restriction
1	Restricted in physically strenuous activity but ambulatory and able to carry out work of a light or sedentary nature, e.g., light house work, office work
2	Ambulatory and capable of all self-care but unable to carry out any work activities. Up and about more than 50% of waking hours
3	Capable of only limited self-care, confined to bed or chair more than 50% of waking hours
4	Completely disabled. Cannot carry on any self-care. Totally confined to bed or chair
5	Dead

As per Oken, 1982.

[figure not shown]
6.4 Sample Handling, Storage and Shipment

Detailed instructions for central laboratory sample collection, labeling, processing, storage, and shipping will be provided to the site in the Laboratory Manual.

Samples will be collected for PK, ADA, peripheral WBC population, CD marker expression, and additional renal function studiesFor PK and ADA, WB is to be collected with subsequent serum isolation. Serum samples should be aliquoted and transferred as frozen (–20°C or below, -70°C preferred), according to the Laboratory Manual.

For the analysis of peripheral WBC populations and cell surface markers, WB is to be collected and shipped (ambient), as per the Laboratory Manual, directly to the selected vendor for immediate processing.

ADC Therapeutics ADCT-402
ADCT-402-102 Protocol Amendment 3

7 Statistical and Analytical Plan

Full details of the analysis plan, including a more technical and detailed elaboration of the statistical analyses will be provided in the statistical analysis plan (SAP).

7.1 Safety Endpoints

Safety will be assessed based on AEs, SAEs, treatment discontinuations due to AEs, DLTs, periodic 12-lead ECG recordings, physical examinations, vital signs measurements, ECOG performance status, and hematology, coagulation panel, biochemistry, pregnancy (for women of child-bearing potential), and urinalysis test results.

7.2 Endpoints

7.2.1 Primary Endpoints

- Assessment of DLTs (Section 6.3.1) and determination of the MTD (Section 3.2) for ADCT-402 during Part 1.
- Determination of the recommended dose of ADCT-402 for Part 2 by the DESC.
- Assessment of safety parameters for Part 1 and Part 2 (Section 7.6.1).

